This is a newly developed intervention introduced in Spring 2022, as part of the pilot study undertaken by the current research team. As part of this efficacy study, the intervention will run from April 2023 until April 2025.

CYP will be referred to Remedi via the police and youth justice services on a consent-based voluntary basis. Remedi reports that these CYP frequently have low levels of awareness / understanding / empathic awareness regarding the impact of their behaviours, have problematic issues within their familial setting and face varying levels of challenges regarding

² Remedi ask for further information around these offences to understand the circumstances and whether the CYP was displaying violent behaviour when in possession.

their mental and/or emotional health. In the experience of Remedi, if unsupported these behaviours often result in greater degrees of violence/criminality³.

The RM intervention consists of three components, to provide intensive one to one support for CYP. All CYP in the intervention group will receive the mentoring component but what, if any, other component they receive will be determined by an initial needs assessment of the CYP. This takes place during an initial contact meeting between the mentor and CYP and considers the following areas of a CYP's life: relationships with parents/carers, educational attendance, mental health, self-esteem and peer pressure, emotional regulation, dealing with people in authority. The result of this assessment informs the creation of a support plan for the CYP⁴.

The three components of RM are:

i. Mentoring: This element will last for around 12 weeks, based on 3-4 1-to-1 sessions per week. The content of these sessions is determined through the creation of an 'Action Plan' agreed with the CYP with Specific, Measurable, Achievable, Relevant and Time-bound (SMART) goals and expectations established.

ii. Restorative Justice (RJ): Provision of a full RJ intervention (whether direct or indirect) with harmed individuals identified and willing to take part RJ will be offered and mentioned during the mentoring work to give many opportunities to take part – using Remedi's empathic thinking work during the mentoring. An RJ intervention will not be able take place without an identified or willing victim

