The overarching objective is to explore whether the RM intervention has greater impact than the RC intervention in terms of CYP's contact with the police and emotional and behavioural difficulties. The study has the following research questions:

1. What is the impact of the RM intervention on the contact with the police of CYP who experience it?
 - a. Is this greater than the impact of the RC intervention?
2. What is the impact of the RM intervention on the emotional and behavioural difficulties of CYP who experience it?
 - a. Is this greater than the impact of the RC intervention?
3. Does any impact vary across subgroups, including CYP demographic characteristics (age, sex and ethnicity) and the exact variant of the RM intervention received (which combination of the three elements received; mentoring, restorative-based family support, restorative justice).⁶

To achieve the overarching objective of the impact evaluation, it is necessary that:

- Regular fidelity checks are carried to ensure that the approved protocol is closely followed;
- That the blinding arrangements are in place;
- Data collection is regularly observed for timeliness and consistency;
- The necessary number of CYP recruitment is reached;
- The data are analysed according to the Statistical Analysis Plan.

YEF will not have any role in the collection or interpretation of the data, or in the decision to submit results.

We will be required to provide monitoring information to the funder quarterly on the progress of the study.

⁶ This will be examined via exploratory analyses.

Any changes to the protocol will be logged in a change log following discussion with the provider and funder.

Design

The trial will be a two-armed (RM and RC) individually randomised controlled trial. Upon referral to Remedi, CYP who have committed a violent offence or have displayed violent behaviours will be randomly assigned to RM (the treatment group) or RC (the control group) on a 1:1 basis.

Table 1: Randomized Control Trial protocol

Step 1:	CYP is referred to Remedi
Step 2:	Remedi assesses eligibility. Ineligible cases are excluded.
Step 3:	Informed consent/assent is provided by eligible CYP.
Step 4:	Data on CYP are collected (SDQ, SRDS questionnaires).
Step 5:	Randomisation done by the University of Birmingham: CYP is assigned to RM or RC.
Step 6:	CYP receives RM or RC.
Step 7:	Right after the interventions are completed, data on CYP are collected (SDQ, SRDS questionnaires) for short-term outcomes.

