The intervention will be offered to CYP aged 10-17 who have committed a violent offence or have displayed violent behaviour identified by the police and youth justice services. The diagram below provides a summary of the stages of the intervention and anticipated numbers of CYP participating in the intervention.

Figure 5. Intervention and control group process summary

The following inclusion and exclusion criteria will be used. Referrals will consist of any young person (10-17) in receipt of a police outcome, up to and including an out of court

disposal (at any level⁷) that has committed a violent offence in Greater Manchester. Once referred to Remedi, CYP must provide written, informed consent (or assent if relevant) before any study procedures occur. The same process would apply for parents/carers of CYP. CYP who are unable to take part or who fail to engage with the intervention would be excluded from the study. In addition, CYP should not participate in other youth support programmes at the same time as the RM or RC intervention.

We will request both CYP assent and their parents/carers' consent in line with Remedi's processes to involve CYP and their carers in the consenting process. The only exception to this would be 17-year-olds living independently, of who there are expected to be few.

Trained Remedi mentors will introduce the trial to CYP who will explain the main aspects of the mentoring programme. CYP and their parents/carers will also receive information sheets. Mentors will discuss the trial with CYP in light of the information provided in the information sheets. CYP and their parents/carers will then be able to have an informed discussion with the mentor. Mentors will obtain written assent (and consent where applicable) from CYP and written consent from parents/carers willing to participate in the trial.

Police and Youth Justice services will identify and refer CYP cases satisfying the above criteria to Remedi. The mentoring meetings, which include data collection, will take place in Greater Manchester, in the buildings of local authorities and the Greater Manchester Police. The questionnaire data will be transferred to the Remedi case management system by the mentors. The police administrative data will be collected by appropriately authorised Remedi staff that will be given access to a police computer.

Sample size calculations

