- Contamination (external factors influencing outcomes) – monitor whether other programs are being offered to CYP.

3. *To inform the analysis and reporting it is necessary to:*

- Document all threats to internal validity registered during the intervention.

4. *To inform generalizability and scaling-up it is necessary to:*

- Collect data on the costs and context of the intervention.

Analysis

Descriptive statistics will be presented for the overall sample, as well as for the treatment and control groups separately. The random assignment of cases will be formally tested by comparing means of observable characteristics (such as age, sex, ethnicity among others) between treatment and control groups.

For the analysis, simple differences in means will be calculated for all the outcomes as well as regression-adjusted results. An intention to treat effect (ITT), denoted by β , will be estimated in the regression model presented below:

$$E(Y_i|T_i, Z_i) = \alpha + \beta T_i + Z_i' \gamma$$

Y_i is the outcome for individual i . T_i is an indicator variable equal to 1 if i was assigned to treatment and 0 if i was assigned to the control group. Z_i is a vector of individual characteristics that are not affected by the intervention (such as sex, age, ethnicity, district, past offences, and referral source). The analysis below depends on the overarching assumption that the sample of observations are independent to each other. This is reasonable as the sample is only a small subset of the whole population.

The dependent variable here is a count variable and it is highly likely that the lower values will have much higher frequency, in other words it is heavily skewed to the right. This feature of the data suggests that they are best analysed using Poisson regression.

Another assumption that needs to hold for the Poisson regression is that conditionally on the regressors, the mean and variance of Y_i must be equal to each other. If this assumption does not hold, then we must estimate the model using the Negative Binomial regression which is able to deal with overdispersion.

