We will collect cost data using the principles articulated in the YEF guidance document, i.e. a bottom up approach estimating the different components of costs for the organisation concerned. We expect to collect the data from Remedi and include labour costs (these will be the main source of costs), material (including licensing) costs, training costs, and venue costs where applicable (if this is a regular fixed rental to be paid where say mentoring takes place). There is certainty about some of these costs, such as labour because the staff have already been hired, and in the event of excess demand for the interventions, no new staff will be hired to meet this demand.

Diversity, equity and inclusion

We are an experienced and diverse team with extensive experience of ensuring that the research designs consider diversity and inclusion. All team members have undertaken mandatory institutional EDI training.

We will ensure that each phase is delivered in a culturally competent way and does not exclude people for cultural and linguistic reasons. For example, we have made clear to Remedi staff and on participants information sheets that study information can be provided in different formats (such as audio) or languages as needed. Our design also seeks to collect data on all CYP referred to the Remedi service, regardless of their experience of it (positive or negative). Remedi have also agreed to offer interviews to all CYP who complete the intervention. Through including the voices of the CYP, as well as all other relevant participant groups, in the study and being culturally aware when we speak to them, we will ensure their voices are truly included in the evaluation. We will also monitor the participants background to flag any wide discrepancies with the demographic composition of the areas served. This will be done both through discussions with relevant project stakeholders, including Remedi staff and referral partners, as well as quantitative analysis That should ensure the research design is truly inclusive by accounting for the potential diverse voices.

Ethics and registration

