### **Missing data**

The primary outcome analysis will be performed according to the ITT principle (described above). The primary outcome is measured by police administrative data and therefore outcome variables for CYP that have disengaged with the intervention will still be collected, reducing concerns of missing values for the primary outcome variable. For the control variables that might be missing, we will follow YEF guidelines and in a first step we will attempt to establish the mechanism behind missingness using a logistic regression model. Depending on the pattern of missing data, either multiple imputation or sensitivity analyses will be conducted.

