### **Compliance**

The evaluation has been designed to engage CYP in both treatment and control groups. Implementation of the intervention will be monitored to make sure that compliance is near

perfect by introducing a fidelity check agreement. However, it is expected that some CYP might disengage, justifying the ITT and LATE analysis proposed in the analysis section above.

The ITT approach analyses CYP based on their original group assignments, irrespective of whether they completed the treatment or not. The LATE approach estimates the effect of the treatment exclusively for CYP who comply with their assigned treatment, defined as (J-PAL, 2023):

$$LATE = \frac{E(Y_i|z_i = 1) - E(Y_i|z_i = 0)}{E(d_i|z_i = 1) - E(d_i|z_i = 0)} \quad (3)$$

Where  $Y$  is the outcome for CYP  $i$  (as specified above);  $z$  represents the treatment assignment, with a value of 1 if the CYP was assigned to treatment (RM) and 0 otherwise;  $d$  represents whether the treatment was received, equal to 1 if the CYP engaged with treatment and 0 otherwise. In this equation, random treatment assignment serves as an instrumental variable for the status of treatment. As we have available data on the number of sessions received by each CYP we will define  $d_i = 1$  if the CYP completes the full intervention.

The LATE estimation relies on a few assumptions. The first is the independence assumption that is automatically satisfied because of random assignment of the treatment. The estimation also requires a positive fraction of compliers and that the monotonicity (being assigned to treatment does not reduce the likelihood of being treated) and exclusion restriction assumptions (CYP respond to the treatment directly, rather than just to their assignment to receive it, therefore treatment assignment does not change the outcome) hold (J-PAL, 2023). In addition, we assume that compliance does not vary with treatment assignment. The experimental design, which ensures perfect blindness, guarantees that this assumption holds true. In other words, CYP who consent to participate in the intervention do not know whether they are going to receive RM or RC (Gerber, Green, Kaplan and Kern, 2010; EGAP).

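### The protocol's exclusion of CYP who fail to engage can only act after randomisation and conflicts with the planned ITT analysis; the two must be reconciled before the police data are extracted

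*Protocol*

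**What the plan says.** The inclusion and exclusion criteria (protocol, Participants) state that "CYP who are unable to take part or who fail to engage with the intervention would be excluded from the study". No time point is attached.

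Protocol Table 1 gives the order of events. Eligibility is step 2, consent step 3 and baseline questionnaires step 4. Step 5 reads "Randomisation done by the University of Birmingham: CYP is assigned to RM or RC" and step 6 reads "CYP receives RM or RC".

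On analysis, the protocol (Analysis) specifies an ITT effect by assigned arm, with a LATE analysis added because compliance is not expected to be perfect. The SAP agrees. Its Compliance section says "The ITT approach analyses CYP based on their original group assignments, irrespective of whether they completed the treatment or not", and its Missing data section says that, for the primary outcome, "outcome variables for CYP that have disengaged with the intervention will still be collected". The protocol's section on diversity, equity and inclusion points the same way: "Our design also seeks to collect data on all CYP referred to the Remedi service, regardless of their experience of it".

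The arms make very different demands. Of RM mentoring, the protocol (Intervention) says "This element will last for around 12 weeks, based on 3-4 1-to-1 sessions per week". RC is four sessions, spread over one to four weeks (protocol, Control Group).

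**The concern.** A CYP cannot fail to engage with RM or RC before being given one of them. Read with Table 1, the criterion removes randomised participants for behaviour after allocation, which is what an ITT analysis is meant to prevent. The protocol and the SAP cannot both be followed to the letter.

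Two things could be lost if the exclusion were applied. The first is the protection of randomisation: if different numbers or kinds of CYP drop out of a long, intensive arm and a short, light one, the remaining groups are no longer comparable. The second is much of the LATE analysis, which needs CYP who were assigned to RM but did not receive it in full.

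There is a practical route by which this could happen. Remedi staff collect the police data (protocol, Participants), and Remedi's closed-case status defines completion (SAP, Compliance, footnote 4). The logic model expresses the planned scale as 176 CYP engaged in each arm. An extract built on that basis could omit disengaged CYP before any analyst applies ITT.

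**Working it through.** **1. The rules side by side**

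| Source | Randomised CYP who does not engage |
|---|---|
| Protocol, Participants | Excluded from the study |
| Protocol, Analysis | In the ITT estimate, by assigned arm |
| SAP, Missing data | Police outcome still collected |
| SAP, Compliance | Analysed in the original arm |
| Protocol, Table 4 | Police data on N = 352, the full planned sample |

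No section limits the exclusion to the period before randomisation, or says that it means only stopping delivery.

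**2. The planned sample size**

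Inputs (protocol Table 3): d = 0.3, two-sided alpha 0.05, power 0.80, 1:1 allocation. The normal approximation, n per arm = 2(1.960 + 0.842)²/0.3², gives 175. The noncentral t calculation gives 176 (power 0.801), so 352 reproduces. It has no allowance for exclusions: it assumes that everyone randomised is analysed.

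Power after removal is Φ(0.3·√[n₁n₀/(n₁+n₀)] − 1.96):
- nobody removed, 176 v 176: 0.80
- 20% removed from each arm, N = 282: 0.71
- 30% of RM and 10% of RC removed, 123 v 158: 0.70

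The removal rates are assumptions.

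**3. Could removal differ by arm?**

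Assume the same weekly chance w of disengaging in both arms, so the proportion lost is 1 − (1 − w)^weeks.
- w = 2%: RM over 12 weeks loses 21.5%; RC over 1 to 4 weeks loses 2.0% to 7.8%.
- w = 3%: RM loses 30.6%; RC loses 3.0% to 11.5%.

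Unequal length alone can therefore produce unequal removal. The documents give no actual rates, and the weekly figures are assumptions.

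**4. Bias with no true effect**

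Assumptions: 30% of RM and 10% of RC are excluded. A fraction h = 0.3 of CYP is higher-risk, with r times the contact rate of the rest, and is m times as likely to be excluded. For an arm with excluded fraction f:

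- exclusion probability in the rest: p = f/(mh + 1 − h)
- mean among the retained, relative to the rest: [h(1 − mp)r + (1 − h)(1 − p)]/(1 − f)

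The absolute mean cancels from the ratio. For r = 2 and m = 2:
- RM: p = 0.30/1.3 = 0.2308; retained mean = (0.1615×2 + 0.5385)/0.70 = 1.231
- RC: p = 0.10/1.3 = 0.0769; retained mean = (0.2538×2 + 0.6462)/0.90 = 1.282
- rate ratio = 1.231/1.282 = 0.96

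Extreme case, r = 2 with every exclusion from the higher-risk group: RM retains only the rest (mean 1); RC retains (0.2×2 + 0.7)/0.9 = 1.222; rate ratio = 0.82.

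| r | m = 2 | m = 3 | all exclusions from higher-risk group |
|---|---|---|---|
| 1.25 | 0.99 | 0.98 | 0.95 |
| 1.5 | 0.98 | 0.96 | 0.90 |
| 2 | 0.96 | 0.93 | 0.82 |

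With m = 1 the ratio is 1. It is also 1 if the excluded fraction and the selection are the same in both arms. If disengagers had less police contact than the others, the bias would run against RM.

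**The case against.** The strongest reply is that the documents already settle the analysis. The protocol's Impact evaluation section requires the data to be analysed according to the SAP. Version 1.5 of the protocol (30/4/2024) was issued to bring it into agreement with the SAP (latest version 6/2/2024), so its later date does not mean that its wording prevails. The protocol itself plans ITT and LATE, monitors CYP who disengage, and lists police data for all 352. On this view, one enrolment sentence is left over among consistent analysis text. That stands as far as it goes: if the SAP is followed for everyone randomised, the bias does not arise.

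It is also fair that being excluded from the study is not defined as being left out of the ITT set, and that the part about CYP unable to take part may be a screen before randomisation. I could not see Figure 5, which may place the exclusion in time. But the step order leaves no pre-randomisation reading for failure to engage with the intervention, and the update that was meant to align the documents left the sentence in.

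A reader might go further and infer that the primary analysis is not ITT, or that RM will be flattered by an amount equal to the whole effect the SAP targets (1/1.22 = 0.82). The documents support neither. No section gives engagement by arm or by risk, so differential removal is plausible but not shown, and 0.82 needs RM to lose all of its higher-risk CYP and nobody else. The SAP assumes that compliance does not vary with assignment. Its reason, that CYP do not know their arm at consent, does not cover disengagement after allocation, but that gap does not show that the arms will differ.

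**Conclusion.** The contradiction is real and should be corrected: as written, the protocol excludes randomised CYP for behaviour after allocation, while both documents plan ITT. It does not show that the planned primary analysis is biased. Harm depends on the exclusion being applied to the study population or the police extract.

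If it were applied, unequal removal is plausible given the arms' lengths, and the bias would favour RM if disengagers have more police contact. With 30% and 10% excluded and a 30% higher-risk group at twice the contact rate, the spurious rate ratio is about 0.96 when that group is twice as likely to be excluded. The value of 0.82 is the extreme case. All of these inputs are assumptions. Power would also fall, to about 0.70 in that scenario, because 352 contains no allowance for exclusions.

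**What to change.** - In the protocol's Participants section, limit the exclusion to CYP screened out before randomisation.
- State in both documents that every randomised CYP, except where consent for data use is withdrawn, stays in the police-data extract and is analysed in the allocated arm. Participation is voluntary and consent-based, so the exception is needed.
- State that non-engagement enters only the LATE analysis.
- State when the follow-up window starts for CYP who do not complete. Both documents count the three months from completion or the end of the intervention, which gives non-completers no clear starting date.

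The cost is a few sentences. No extra data source is needed, because the SAP already plans to collect police outcomes for disengaged CYP. The wording should be settled before the extract is made, and whoever makes it should work from the full randomisation list.

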We are particularly aware of risks related to Covid-19; the team and the university has become proficient with secure online working, including online meetings, webinars and workshops. The team has access to standard software such as Microsoft Teams for this purpose if needed.

Additionally, given the increased possibility of illness or care duties, a resilient team has been created. Each evaluation in addition to a lead, has at least two senior researchers and two research fellows associated with it. We also have a small cohort of experienced persons who have an advisory role who can step in for a team member should there be an unexpected contingency that will make them unavailable. All the senior researchers supporting the overall project lead have the ability and experience in this area to step in to become overall lead in case of anything unexpected happening that makes the project manager unable to carry on leading the project.

Our issues log will be used to collate key questions/issues and target the appropriate individual for a response which will be recorded in the log. Our risk register will identify, assess and control risks and uncertainties enabling us to improve the ability of the project to succeed. Our risk management is based on PRINCE2 principles.

We believe this is a low to medium risk project and have identified (and mitigated for) a small number of potential early risks prior to project initiation. The issues log and risk register will be reviewed weekly by the research team. Any issues and/or risks will be shared at the earliest possible opportunity internally for mitigation and where necessary, if these are viewed as major risks, these will be escalated to ‘named’ project contacts within YEF and Remedi.

Timeline

Dates	Activity	Staff responsible/ leading
April–May 2023	
Project mobilization – staff recruitment, training, CYP consenting process, update record management processes
 
Evaluation mobilization – finalise evaluation materials (topic guides, fidelity checklist), draft protocol and statistical analysis plan.
	
Remedi
 
UoB

May 2023	Project launch – recruitment of CYP into intervention and control group, begin collecting case monitoring data, begin collecting SDQ/SRDS outcome measures.	
Remedi
 
UoB

November 2023	Submit final, peer reviewed trial protocol and Statistical Analysis Plan.	UoB
May 2023– June 2025	
Project operation.
 
Key dates:
 
 • CYP consented into the study until 30 November 2024 Delivery ends late February / beginning of March 2025 (for CYP randomised into RM) – closing SRDS / SQDs completed. • Opening, closing and 6-month follow-up SDQs/SRDSs, and Remedi case monitoring data to be gathered on an ongoing basis by Remedi staff throughout the efficacy study. Final data to be shared by 31 March 2025. • CYP (consented up until 31 July 2024) approached to complete 6-month follow-up SDQs/SRDS (ends in May 2025). • GMP data collection undertaken by: 6 June 2025. 
UoB team to gather qualitative data (interviews with staff, referrers, CYP, families, RJ victims) on an ongoing basis throughout the efficacy study, until end May 2025.
	
Remedi
 
UoB

July 2025	Draft final evaluation report	UoB
Sept 2025	Submit final evaluation report	UoB
Oct 2025	Complete support for YEF publication process	UoB

TBC	Data archiving	UoB
-----	----------------	-----

References

Angrist, J. D. (2014). Instrumental Variables (Take 2): Causal Effects in a Heterogeneous World. Delivered as part of MIT 14.387.

Dakof, G. A., Henderson, C. S., Rowe, C. L, Boustani, M., Greenbaum, P., Wang, W., Hawes, S., Linares, C., & Liddle, H. A. (2015). A randomized controlled trial of multidimensional family therapy in juvenile drug court. *Journal of Family Psychology*, 29, 232-241. doi: 10.1037/fam0000053

Darnell, A. J., and Schuler, M. S. (2015). Quasi-Experimental Study of Functional Family Therapy Effectiveness for Juvenile Justice Aftercare in a Racially and Ethnically Diverse Community Sample. *Children and Youth Services Review*, 50, 75-82. doi:10.1016/j.childyouth.2015.01.013.

DuBois, D. L., Holloway, B. E., Valentine, J. C., & Cooper, H. (2002). Effectiveness of mentoring programs for youth: A meta-analytic review. *American Journal of Community Psychology*, 30, 157–197.

Duflo, Esther, Rachel Glennerster, and Michael Kremer. (2008). Using Randomization in Development Economics Research: A Toolkit. T. Schultz and John Strauss, eds., *Handbook of Development Economics*. Vol. 4. Amsterdam and New York: North Holland.

